15.2.1 All Adverse Events

Population: SAF Analysis Set

Adverse events will be summarized by worst severity (according to NCI-CTCAE version 5.0) per subject, using the most recent available MedDRA version (21.1 or higher) PT as event category and primary SOC body term as Body System category.

Frequency tables for AEs captured on the “Adverse Events” eCRF pages will be based on TEAEs as defined above.

A first overview table of adverse events will be provided by dose level and overall by summarizing the number and percentage of participants with any:

- TEAE
- TEAEs related to trial treatment, (i.e. peposertib, RT, or capecitabine)

- TEAEs related to peposertib
- TEAEs related to RT
- TEAEs related to capecitabine
- Serious TEAE
- Serious TEAE related to trial treatment (i.e. peposertib, RT, or capecitabine)
- Serious TEAEs related to peposertib
- Serious TEAEs related to RT
- Serious TEAEs related to capecitabine
- TEAEs with grade ≥ 3
- TEAEs with grade ≥ 4
- TEAEs with grade ≥ 3 related to trial treatment (i.e. peposertib, RT or capecitabine)
- TEAEs with grade ≥ 4 related to trial treatment (i.e. peposertib, RT or capecitabine)
- TEAEs with grade ≥ 3 related to peposertib
- TEAEs with grade ≥ 4 related to peposertib
- TEAEs with grade ≥ 3 related to RT
- TEAEs with grade ≥ 4 related to RT
- TEAEs with grade ≥ 3 related to capecitabine
- TEAEs with grade ≥ 4 related to capecitabine
- TEAEs leading to dose modification of any trial treatment (i.e. peposertib, RT or capecitabine)
- TEAEs leading to dose modification of peposertib
- TEAEs leading to dose modification of RT
- TEAEs leading to dose modification of capecitabine
- TEAE leading to death
- TEAE leading to death related to trial treatment, peposertib, RT or capecitabine
- TEAE leading to death related to peposertib
- TEAE leading to death related to RT
- TEAE leading to death related to capecitabine
- TEAE leading to trial discontinuation

- TEAE leading to temporary discontinuation of at least one trial treatment
- TEAE leading to temporary discontinuation of all trial treatments
- TEAE leading to temporary discontinuation of M3814
- TEAE leading to temporary discontinuation of RT
- TEAE leading to temporary discontinuation of Capecitabine
- TEAE leading to permanent discontinuation of at least one trial treatment
- TEAE leading to permanent discontinuation of all trial treatments
- TEAE leading to permanent discontinuation of M3814
- TEAE leading to permanent discontinuation of RT
- TEAE leading to permanent discontinuation of Capecitabine

Frequency tables summarizing events in the following categories will be prepared by dose level and overall, sorted by alphabetical order of SOC and PT:

- TEAEs
- TEAEs related to trial treatment (i.e. peposertib, RT, or capecitabine)
- TEAEs related to peposertib
- TEAEs related to RT
- TEAEs related to capecitabine
- Serious TEAEs
- TEAEs excluding SAEs, with overall frequency $\geq 5\%$ by SOC and PT (threshold will be applied on PT)
- Serious TEAEs related to trial treatment
- Serious TEAEs related to peposertib
- TEAEs by worst CTCAE grade: any grade (including AEs with missing grade), grades ≥ 3 , ≥ 4 and 5
- TEAEs related to trial treatment by worst CTCAE grades: any grade (including AEs with missing grade), grades ≥ 3 , ≥ 4 and 5
- TEAEs related to peposertib by worst CTCAE grades: any grade (including AEs with missing grade), grades ≥ 3 , ≥ 4 and 5
- TEAEs related to RT by worst CTCAE grades: any grade (including AEs with missing grade), grades ≥ 3 , ≥ 4 and 5

- TEAE related to capecitabine by worst CTCAE grades: any grade (including AEs with missing grade), grades ≥ 3 , ≥ 4 and 5
- TEAEs leading to death

In addition, all TEAEs and TEAEs related to peposertib with at least 2 participants will be summarized in two tables sorted by frequency (descending order) and PT.

The following listings will be produced based on the “Adverse Events” eCRF page:

- All AEs (whether treatment-emergent or not)
- Serious TEAEs related to any trial treatment
- TEAEs within 6 weeks after surgery and delayed surgery

These listings will include the following items:

- Dose level
- Subject identification number
- Age
- Sex
- Race
- First and last dose date for peposertib, RT and capecitabine
- Reported Term with SOC and PT
- Start, change and end date with their corresponding treatment day
- Treatment Emergent Adverse Events flag (N/Y; only for the listing of all AEs)
- Timing related to treatment (if same day of treatment administration)
- TEAE related to peposertib flag (N/Y)
- TEAE related to RT flag (N/Y)
- TEAE related to capecitabine flag (N/Y)
- Serious Adverse Events flag (N/Y; only for the listing of all AEs)
- DLT flag (Y/N)
- CTCAE Grade
- Action taken with peposertib, with RT and with capecitabine
- Outcome of AE
- AE occurred after COVID-19 pandemic start (Y/N).

Evaluation of COVID-19 effects on AEs

The direct effect of COVID-19 for AEs will be assessed via listing of COVID-19 related AEs. The following listing will be generated using the ‘COVID-19 related terms MedDRA 23.0 update Spreadsheet’, considering all ‘search terms for COVID-19-related’ =’Y’. Same information as for the listing of all AEs will be provided.

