In conclusion, emerging clinical safety data from studies EMR100036-001 and EMR100036-002, and supportive results of a comprehensive series of nonclinical safety pharmacology, PK, and toxicology studies, as well as primary and secondary PD findings support continued clinical development of peposertib in combination with RT, and/or chemotherapy.

3 Objectives and Endpoints

Study objectives and endpoints are provided in [Table 6](#). Statistical analysis of the endpoints is described in [Section 9.4](#).

Table 6 Study Objectives and Endpoints

Objectives	Endpoints (Outcome Measures)	Endpoints (Outcome Measures) Timeframe
Primary		
To define an MTD and RP2D of peposertib in combination with capecitabine and RT	Occurrence of dose limiting toxicities	Time from first study intervention to the end of CRT with a final assessment at 4 weeks after surgery
Secondary		
To evaluate safety and tolerability of peposertib in combination with capecitabine and RT	
 • Occurrence of TEAEs and treatment-related adverse events according to the NCI-CTCAE version 5.0 • Occurrence of abnormalities (Grade ≥ 3) in laboratory test values, markedly abnormal vital sign measurements, and clinically significantly abnormal ECGs including clinically important increases in QT interval (QTcF) 	Time from first study intervention to final assessment at 1 year
To explore antitumor activity of peposertib in combination with capecitabine and RT	
 • Composite endpoint of pCR/cCR • Disease-free Survival • pCR • cCR • Local recurrence and/or distant metastasis • Neoadjuvant rectal score 	
 • Pathology evaluation of specimen after surgery (pCR) and clinical evaluation 1 to 2 weeks prior to surgery (cCR) • Time from first study intervention to final assessment at 1 year • Pathology evaluation of specimen after surgery • Time from first study Intervention until clinical evaluation 1 to 2 weeks prior to surgery • Time from surgery to final assessment at 1 year • Pathology evaluation of specimen after surgery
To assess the PK of peposertib	PK profile of peposertib in terms of PK parameter estimates (e.g. C _{max} , AUC _{0-t} , t _{max} , CL/f, Vz/f, t _{1/2})	FD1 and FD9

CCI

cCR=Clinical Complete Response, CRT=chemoradiotherapy, CCI [REDACTED]
[REDACTED] ECG=electrocardiogram, FD=fraction day, MTD=maximum tolerated dose, NCI-CTCAE=National Cancer

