8.3 Adverse Events and Serious Adverse Events

The definitions of an AE and a serious adverse event (SAE) are in [Appendix 7](#).

8.3.1 Time Period and Frequency for Collecting Adverse Event and Serious Adverse Event Information

The AE reporting period for safety surveillance begins when the participant is initially included in the study (date of first signature of informed consent/date of first signature of first informed consent) and continues until the final assessment at 1 year. Any AE assessed as not related to study intervention will be recorded only up to the short-term safety follow-up period. Any AE assessed as related to study intervention will be recorded up to resolution or permanent outcome, irrespective of the time elapsed since the last administration of study intervention.

Any SAE assessed as related to study intervention must be recorded and reported, as indicated in [Appendix 7](#), whenever it occurs, irrespective of the time elapsed since the last administration of study intervention. Any SAE assessed as not related to study intervention must be recorded and reported, as indicated in [Appendix 7](#), only up to Week 27 in the long-term safety follow-up period.

The method of recording, evaluating, and assessing causality of AEs (including SAEs) and the procedures for completing and transmitting SAE reports are in [Appendix 7](#).

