9.4.2 Safety Analyses

Statistical analysis methods for safety endpoints are described in [Table 13](#).

Table 13 Statistical Analysis Methods for Safety Endpoints

Endpoint	Statistical Analysis Methods
Primary	
Occurrence of DLTs	The number and proportion of participants experiencing a DLT confirmed by the SMC during the DLT period will be reported by dose level. Analysis will be based on the DE Analysis Set.
Secondary	
Occurrence of TEAEs and treatment-related AEs according to the CTCAE version 5.0	All AEs will be coded according to the MedDRA, version 21.0 or higher. The severity of AEs will be graded using NCI-CTCAE v5.0 toxicity grades. Adverse events related to study intervention will be defined as any AE considered related to any study intervention. In addition, missing classifications concerning study intervention relationships will be considered related to the study intervention(s). Adverse events observed from the first dose until 30 days after last study intervention administration (i.e. TEAEs) will be summarized according to MedDRA system organ classes and preferred terms. The incidence and type of the following will be analyzed: 
 • TEAEs and SAEs • TEAEs and SAEs related to study intervention • TEAEs with NCI-CTCAE Grades ≥ 3 • TEAEs related to study intervention with NCI-CTCAE Grades ≥ 3 • AEs leading to withdrawal, dose modifications, or permanent study intervention discontinuation • Deaths and reasons for death will be tabulated. In addition, deaths within 30 days from last dose administration and deaths beyond this period up to 90 days follow-up and reasons for death will be tabulated. Analyses will be based on the Safety Analysis Set.

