The purpose of this integrated analysis plan (IAP) is to document technical and detailed specifications for all analyses of data collected for the Phase Ib (dose escalation) protocol MS100036-0020. Results of the analyses described in this IAP will be included in the clinical study report (CSR). Additionally, the planned analyses identified in this IAP may be included in regulatory submissions or future manuscripts. Any post hoc, or unplanned analyses performed to

provide results for inclusion in the CSR but not identified in this prospective IAP will be clearly identified in the CSR.

The IAP is based on Section 9 (Statistical considerations) of the study protocol and protocol amendments and is prepared in compliance with International Conference on Harmonization (ICH) guideline E9.

Separate IAPs will document technical and detailed specifications for the analyses to be provided for safety monitoring committee (SMC) meetings.

Peposertib instead of peposertib (M3814) will be used in the current document.

5 Objectives and Endpoints

Objectives	Endpoints (Outcome Measures)	Endpoints (Outcome Measures) Timeframe	IAP section
Primary			
To define an MTD and RP2D of peposertib in combination with capecitabine and RT	Occurrence of dose limiting toxicities (DLT)	Time from first study intervention to end of chemoradiotherapy with a final assessment at 4 weeks after surgery	15. Safety Analyses
Secondary			
To evaluate safety and tolerability of peposertib in combination with capecitabine and RT	Occurrence of TEAEs and treatment-related adverse-events according to the NCI-CTCAE version 5.0 Occurrence of abnormalities (Grade ≥ 3) in laboratory test values, markedly abnormal vital sign measurements, and clinically significantly abnormal ECGs including clinically important increases in QT interval (QTcF)	Time from first study intervention to final assessment at 5 years	15. Safety Analyses
To explore antitumor activity of peposertib in combination with capecitabine and RT	Composite endpoint of pCR/cCR	Pathology evaluation of specimen after surgery (pCR) and clinical evaluation 1 to 2 weeks prior to surgery (cCR)	14. Efficacy Analyses

Objectives	Endpoints (Outcome Measures)	Endpoints (Outcome Measures) Timeframe	IAP section
	Disease-free Survival	Time from first study intervention to final assessment at 5 years	
	pCR	Pathology evaluation of specimen after surgery	
	cCR	Time from first study intervention until clinical evaluation 1 to 2 weeks prior to surgery	

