Percent change from baseline: $100 * (visit value - baseline value) / baseline value$

Definition of on treatment period:

On treatment period is defined as the time from the first administration of study intervention to the last administration of study treatment + 30 days, or the clinical cut-off date (if the treatment is still ongoing), or death, whichever occurs first.

Date of last known to be alive

The date of last known to be alive will be derived for participants not known to be dead at the analysis cut-off using the latest complete date among the following:

- All subject assessment dates:

- Laboratory assessments using information from “Hematology”, “Biochemistry”, “Coagulation”, “Urinalysis”, “Pregnancy test” and “Creatinine Clearance” eCRF pages (LBDTC variable from LB SDTM domain to be used)
- Vital signs using information from “Vital signs” eCRF page (VSDTC variable from VS SDTM domain to be used)
- Performance status using “ECOG Performance status” eCRF page (QSDTC variable from QS SDTM domain to be used)
- ECG, using information from both local and central ECGS (EGDTC variable from EG SDTM domain to be used)
- Tumor assessments using “Tumor assessments” eCRF pages (TRDTC/TUDTC variable from TR/TU SDTM domain to be used)
- Surgery information using “Rectal Surgery at week 15”, “Rectal Surgery after Week 15”, “Surgery after discontinuation” eCRF pages
- Anti-cancer treatment after discontinuation start and end date from “Anti-Cancer treatment after discontinuation” eCRF page.
- Start dates of concomitant medications or anti-cancer therapies administered after study treatment termination using “Concomitant medications”, “Anti-cancer treatment after discontinuation details” eCRF pages (CMSTDTC variable from CM SDTM domain to be used)
- AE start dates from “Adverse events details” eCRF page (AESTDTC variable from AE SDTM domain to be used)
- Study treatment administration dates using “M3814 (PEPOSERTIB)/PLACEBO Administration Details”, “RT Administration” and “Capecitabine Administration” eCRF pages (EXSTDTC variable from EX SDTM domain to be used)
- Last known to be alive date using “Survival Follow-up page” (SSDTC variable from SS SDTM domain where SSCAT=“SURVIVAL FOLLOW-UP”), where status is “Alive”.

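### The treatment-related adverse event endpoint runs to 1 year, but every related-event incidence table stops 30 days after the last dose

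*SAP*

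**What the plan says.** **Endpoint.** Protocol Section 3, Table 6 (repeated in the synopsis) names TEAEs and treatment-related adverse events as a secondary safety endpoint, with timeframe "Time from first study intervention to final assessment at 1 year". SAP Section 5 lists the same endpoint but still prints "Time from first study intervention to final assessment at 5 years".

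**Collection.** Protocol Section 8.3.1 follows related events beyond treatment: "Any SAE assessed as related to study intervention must be recorded and reported", however long after the last administration. For unrelated events, "Any AE assessed as not related to study intervention will be recorded only up to the short-term safety follow-up period". Unrelated SAEs are collected to Week 27.

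**Planned analysis in the protocol.** Section 9.4.2, Table 13 says: "Adverse events observed from the first dose until 30 days after last study intervention administration (i.e. TEAEs) will be summarized". The list that follows includes "TEAEs and SAEs related to study intervention" and Grade 3 or higher related TEAEs.

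**Planned analysis in the SAP.**
- Section 9 defines the on-treatment period as "the time from the first administration of study intervention to the last administration of study treatment + 30 days", or to cut-off or death if earlier. Section 15.2 defines TEAEs by onset in that period.
- Section 15.2.1 bases its frequency tables on TEAEs. Every related row or table there is a TEAE item, including "Serious TEAEs related to trial treatment".
- Section 15.2.3 covers events starting after the on-treatment period. It has one table of all late toxicities by worst grade, a listing of those related to any trial treatment, and a listing of those of Grade 3 or higher.
- Section 15.3.1 tabulates all deaths by reason, with a treatment-related adverse event as one reason.
- Section 15.3.2 summarises SAEs with no causality split and no stated window.

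**The concern.** The protocol gives late radiotherapy toxicity as the reason for keeping participants to 1 year. Its Section 2.3 says that both acute and late toxicity could be more severe when radiotherapy is combined with peposertib. A reader would therefore expect at least one treatment-related rate on the 1-year scale. As planned, the related rates by dose level are short-term rates, although the endpoint they serve is stated to 1 year.

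A related, non-fatal bowel perforation at month 6 would change no related AE or related SAE percentage. It would be counted in the late-toxicity table, where nothing marks it as related, and a reader would have to find it in a listing.

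The 1-year follow-up analysis in SAP Section 6.4 is affected too. The primary cut-off (SAP Section 6.3) comes when the last participant ends short-term follow-up, at about Week 19. Every TEAE window has closed by then, so rerunning the Section 15.2.1 tables at 1 year can add no new-onset event.

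**Working it through.** The documents give no rate or sample-size figure for this point, so there is nothing to reproduce. The check is a calendar comparison.

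**Inputs**
- 25 or 28 fraction days, 5 per week (Protocol Sections 1.3 and 4.1).
- Radiotherapy delay of 0 to 7 days in total (Section 6.6.3.4).
- TEAE window: last dose + 30 days (SAP Section 9).
- Surgery: 15 weeks ± 14 days after start (Protocol Section 4.1.3).
- Late radiotherapy toxicity: 3 months or more after radiotherapy ends (Section 2.3), taken as 91 days.
- 19 participants treated as of 06 May 2021 (synopsis); planned cohorts of 3 (Section 9.2).
- Assumption: fraction day 1 is study day 1 and a Monday.

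**End of the TEAE window**

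| Schedule | Delay | Last dose (day) | Window ends (+30) | Share of 365 days |
|---|---|---|---|---|
| 25 fractions | 0 | 33 | 63 | 17.3% |
| 25 fractions | 7 | 40 | 70 | 19.2% |
| 28 fractions | 0 | 38 | 68 | 18.6% |
| 28 fractions | 7 | 45 | 75 | 20.5% |

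The uncovered part of the year is 365 − 75 = 290 to 365 − 63 = 302 days. Starting on another weekday adds at most one weekend, so the latest end becomes day 77 (77/365 = 21.1%). Stopping treatment early makes the window end sooner.

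**What falls outside it**
- Surgery: 15 × 7 + 1 = day 106. The earliest in-window date is 106 − 14 = day 92, which is 17 days after the latest tabulated window end (day 75).
- Late radiotherapy toxicity without delay: from 33 + 91 = day 124 or 38 + 91 = day 129. A delay moves this later.
- SAP Section 15.2.1 also plans a listing of TEAEs within 6 weeks after surgery. For participants treated and operated on schedule it would be empty, because no TEAE can start after surgery.

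**What the late-toxicity table contains**
- From window end to about Week 19 (19 × 7 + 1 = day 134): related and unrelated events, including surgical complications.
- From Week 19 to Week 27 (27 × 7 + 1 = day 190): related events plus unrelated SAEs.
- After Week 27: new related events only.

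This table cannot be added to the TEAE tables to give participants with any related event by 1 year. A participant may be in both, and the late table is not restricted to related events.

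**Size of one event**
- Cohort of 3: a participant whose only related SAE is late moves the rate from 0/3 to 1/3, or 33 points.
- 19 participants: 1/19 = 5.3 points.
- Illustrative exact 95% intervals at n = 19: 0 events, 0 to 17.6% (upper limit 1 − 0.025^(1/19)); 1 event (5.3%), 0.1 to 26.0%; 3 events (15.8%), 3.4 to 39.6%.

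**The case against.** Several points on the other side stand.

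**The window is the protocol's own.** A reader might infer that the SAP narrowed the endpoint without declaring it in its Section 7. The documents do not support that as the main charge. Table 13 already has the 30-day window and names TEAEs outright for Grade 3 or higher related events. Only the unqualified mention of SAEs in "TEAEs and SAEs related to study intervention" leaves room for a wider reading. The conflict is mainly between Table 6 and Table 13 of the protocol.

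**Collection is not analysis.** A reader might take Section 8.3.1 to mean that the protocol counts related SAEs whenever they occur. It governs recording and reporting and sets no analysis window. It does show that the data will exist.

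**Late related events do not vanish.** They enter the all-causality late-toxicity table and the related listing, and if fatal the death table by reason. The SAP also lists all adverse events, treatment-emergent or not, with relationship flags. Much of the late table after Week 19 is already related-only by the collection rules.

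**The trial is small and descriptive.** With about 19 participants and no hypothesis tests, complete listings carry much of the information. That limits the seriousness of the gap, but a listing does not give the rate that the endpoint names.

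**Late attribution is confounded.** Protocol Section 6.5 allows adjuvant FOLFOX, CAPEOX or capecitabine, started 1 to 3 months after surgery. Late attribution to capecitabine can therefore reflect re-exposure. This is a good reason to keep early and late events in separate columns.

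**Conclusion.** The concern holds in a limited form. Table 6 promises treatment-related events to 1 year, Table 13 summarises adverse events to last dose + 30 days, and the SAP follows Table 13. The related AE and SAE incidence tables therefore cover about 17 to 21% of the endpoint period and end before surgery and before late radiotherapy toxicity as the protocol describes it. Non-fatal related events after that have a listing but no related-event rate.

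It does not follow that late related events go unreported, or that the SAP hid a change.

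The day counts assume a Monday start, full treatment and at most 7 days' delay. The 33- and 5.3-point figures assume that the participant had no related event of the same kind within the window. They use a planned cohort of 3 and a count of 19 that is dated rather than a stated final number. The primary DLT endpoint is unaffected. This is a worthwhile, inexpensive improvement to a secondary safety endpoint.

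**What to change.** 1. Reconcile Table 6 with Table 13 in the protocol, stating which summaries run to last dose + 30 days and which to 1 year. Correct the 5-year timeframe in SAP Section 5.
2. Keep the TEAE tables as they are.
3. Add to SAP Sections 15.2.3 and 15.3.2 a treatment-related version of the late-toxicity table: at least related to any trial treatment and related to peposertib; any grade, Grade 3 or higher, and serious; by dose level and overall.
4. Add the number of participants with any related AE and any related SAE from first dose to 1 year, with onset split at last dose + 30 days. Count each participant once in the total.
5. Flag events that start after adjuvant chemotherapy begins.
6. State the window for the SAE summary in SAP Section 15.3.2.

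The cost is a few tables from data already collected, plus SAP wording and a protocol clarification. The late columns will rest on investigator causality judgements made after surgery and, for some participants, during adjuvant therapy, hence the flag.

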Pharmacokinetic parameter data will be descriptively summarized using: n, Mean, Sd, CV%, Min, Median, Max, geometric mean (GeoMean), and the geometric coefficient of variation (GeoCV) and the 95% confidence interval for the GeoMean (LCL 95% GM, UCL 95% GM). For time to reach maximum observed concentration (t_{max}), only n, Min, Median, and Max will be reported.

If $n \leq 2$, only n, Min, and Max will be reported.

The PK parameter maximum observed plasma concentration (C_{max}) will be reported with the same precision as the source data. All other PK parameters will be reported to 3 significant figures. In export datasets, as well as in the SDTM and ADaM PP domain, PK parameters will be provided with full precision, and will not be rounded. Descriptive statistics of PK parameter data will be calculated using full precision values and rounded for reporting purposes only.

CONFIDENTIAL
INFORMATION

CCI
CCI

17/66

The following conventions will be applied when reporting descriptive statistics of PK parameter data:

Mean, Min, Median, Max, GeoMean, 95% CI: 3 significant digits

Sd: 4 significant digits

CV%, GeoCV%: 1 decimal place

Study day

Study day (also called treatment day) is defined relative to the date of start of treatment (first administration of peposertib, RT, or capecitabine, whatever is earliest). Study day 1 defines the day of first treatment, the day before is defined as study day -1 (no study day 0 is defined).

Definition of baseline

The last measurement prior to first administration of trial treatment (either peposertib, RT or capecitabine) will be used as the baseline measurement. If an assessment is planned to be performed prior to the first dose of study treatment in the protocol and the assessment is performed on the same day as the first dose of study treatment, it will be assumed that it was performed prior to study treatment administration, if assessment time point is not collected or is missing. If assessment time points are collected, the observed time point will be used to determine pre dose on study day 1 for baseline calculation. Unscheduled assessments will be used in the determination of baseline. However, if time is missing, an unscheduled assessment on study day 1 will be considered to have been obtained after study treatment administration.

Definition of change from baseline (per visit)

Change from baseline: visit value – baseline value

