15.2 Adverse Events

Definitions

Treatment-emergent adverse events: those events with onset dates occurring within the on treatment period.

Counting rules and observation periods for AEs during the on treatment period (TEAEs):

- If an AE is reported for a given subject more than once during treatment, the worst severity and the worst relationship to trial treatment will be tabulated.

- Adverse events related to trial treatment are those events with relationship missing, unknown or related to at least one treatment (peposertib, RT or capecitabine).
- Adverse events related to peposertib are those events related to peposertib, regardless of relationship with RT and/or capecitabine
- Adverse events related to RT are those events related to RT, regardless of relationship with peposertib and/or capecitabine
- Adverse events related to capecitabine are those events related to capecitabine, regardless of relationship with peposertib and/or RT
- In case a subject has events with missing and non-missing grades, the maximum of the non-missing grades will be displayed.

For identification of AE treatment emergence, incomplete dates will be handled using the rules presented in Section 0.

Adverse events will be summarized by worst severity (according to NCI-CTCAE version 5.0) per participant, using the latest version of MedDRA preferred term (PT) as event category and MedDRA primary system organ class (SOC) body term as Body System category.

Missing data handling

Incomplete AE-related dates will be handled using the rules presented in Section 0. In case a participant has events with missing and non-missing grades, the maximum of the non-missing grades will be displayed. No imputation of missing grades will be performed.

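### The listing of adverse events after surgery is limited to TEAEs, so for anyone treated and operated on within protocol limits it cannot show an event that starts after surgery

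*SAP*

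**What the plan says.** SAP Section 15.2.1 names three AE listings. One is "All AEs (whether treatment-emergent or not"), one covers serious related TEAEs, and the third is "TEAEs within 6 weeks after surgery and delayed surgery".

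SAP Section 15.2 defines TEAEs as "those events with onset dates occurring within the on treatment period". SAP Section 9 runs that period from the first administration "to the last administration of study treatment + 30 days", or to cut-off or death if earlier. Protocol Table 13 (Section 9.4.2) uses the same limit: "until 30 days after last study intervention administration (i.e. TEAEs"). Protocol Section 6 counts peposertib, capecitabine and radiotherapy as study interventions, so surgery does not extend the window.

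Protocol Section 4.1.3 schedules surgery 15 weeks (± 14 days) after the start of study intervention. It also has surgical morbidity collected at the Week 19 visit, as does the AE note in protocol Table 1.

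The item list for the three listings restricts two flags to the all-AE listing: "Treatment Emergent Adverse Events flag (N/Y; only for the listing of all AEs") and "Serious Adverse Events flag (N/Y; only for the listing of all AEs"). It contains no surgery date.

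**The concern.** The third listing combines two conditions: the event must be treatment-emergent, and it must fall in the six weeks after surgery. If the treatment-emergent window always closes before surgery, no event starting after surgery can satisfy both.

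The protocol deliberately collects AEs from the surgical and postsurgical periods, and this is the one listing in the visible SAP text aimed at them. An empty listing in the study report could be taken to mean that there was no surgical morbidity. A reader who noticed the problem would have to match the all-AE listing against surgery dates held elsewhere (SAP Sections 10.1, 12.4 and 14.1).

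**Working it through.** **Inputs.** 25 or 28 fractions at 5 per week (protocol Section 4.1). At most 7 days of radiotherapy delay in total, with missed fractions made up (Table 10 footnote b; Section 6.6.3.4). Surgery at 15 weeks ± 14 days (Section 4.1.3). TEAE window closing 30 days after the last study treatment (SAP Section 9). Day count as in SAP Section 9: "Study day 1 defines the day of first treatment".

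**1. The protocol's own interval.** 15 − 5.5 = 9.5 weeks from the end of radiotherapy to surgery, as Section 4.1.3 states. For 25 fractions it is 15 − 5 = 10 weeks, as in Section 4.2. Since 9.5 × 7 = 66.5 days, nominal surgery is already 66.5 − 30 = 36.5 days past the TEAE window.

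**2. Close of the TEAE window.** Last treatment day, over Monday to Friday starts, plus 30:

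| Schedule | Last treatment day | TEAE window closes |
|---|---|---|
| 25 fractions, no delay | 33–35 | 63–65 |
| 28 fractions, no delay | 38–40 | 68–70 |
| 25 fractions, 7 calendar days' delay | 40–42 | 70–72 |
| 28 fractions, 7 calendar days' delay | 45–47 | 75–77 |
| 25 fractions, 7 missed and made up | 44–46 | 74–76 |
| 28 fractions, 7 missed and made up | 47–49 | 77–79 |

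The latest close is day 79.

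**3. Scheduled surgery.** Counting elapsed weeks: 1 + 15 × 7 = day 106, and 106 ± 14 = day 92 to 120. Counting instead from the first day of visit Week 15: 14 × 7 + 1 = day 99, and 99 − 14 = day 85 at the earliest.

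**4. Gap.**
- Minimum, elapsed weeks: 92 − 79 = 13 days.
- Minimum, visit-week count: 85 − 79 = 6 days.
- Planned surgery, no delay: 106 − 70 = 36 to 106 − 63 = 43 days.

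**5. What an overlap would need.** A last treatment on day 92 − 30 = 62 or later, which is 62 − 40 = 22 days after the latest undelayed finish. On the visit-week count it is day 85 − 30 = 55, or 55 − 40 = 15 days after. The permitted delay takes the last treatment no later than day 49. Table 10 footnote b and Section 6.6.3.4 word the consequence of exceeding 7 days differently (peposertib; study intervention), but these figures do not depend on which applies.

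**6. How far recording reaches after surgery.** Protocol Section 8.3.1 records unrelated AEs only to the end of short-term follow-up (unrelated SAEs to Week 27). Table 1 gives surgery and the Week 19 visit ± 14 days each. Surgery on day 120 with a visit on day 1 + 19 × 7 = 134 leaves 134 − 120 = 14 days recorded and 42 − 14 = 28 days not. SAP Section 12.4 lists rectal surgery after Week 15 with no upper limit, so such surgery may follow the visit altogether.

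**The case against.** **The wording may be loose.** The SAP does use the term loosely elsewhere. The same item list applies relatedness flags labelled as TEAE flags to the all-AE listing, and SAP Section 15.3.1 puts a TEAE yes/no flag in a listing that should hold only TEAEs. A drafting slip is plausible. But Section 15.2.1 separates all AEs from TEAEs in one list and drops the TEAE flag from the post-surgery listing, so a programmer following the text would apply the filter. A slip needs correcting all the same.

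**Entries are possible.** The listing does not say that onset must follow surgery, and it shows start, change and end dates. A TEAE ongoing or changing after surgery could be listed on a broader reading. This stands, and it is why the conclusion concerns events that start after surgery. Surgery brought forward after early discontinuation could also give entries. That surgery has its own eCRF page, and nothing shows that the listing draws on it. Even then the listing would stop 30 days after the last dose, short of six weeks after surgery.

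**The events are reported elsewhere.** This also stands. A reader might infer that post-surgical events are lost from the report, but the documents do not support that. The all-AE listing holds them. The late-toxicity outputs (SAP Section 15.2.3) hold those that are new, recur after a gap or worsen, with the listings further limited to related or grade ≥ 3 events. SAP Section 15.3 covers deaths and SAEs. SAP Section 18.2 refers to a Clavien-Dindo term file, but the visible text does not show how it is used, so it neither fills the gap nor shows that nothing does.

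**Conclusion.** The listing is wrong as specified. For participants treated and operated on within protocol limits, the TEAE window and the six weeks after surgery do not overlap, so no AE starting after surgery can appear. The minimum gap is 13 days if 15 weeks means elapsed weeks, as Section 4.1.3 words it, and 6 days on the visit-week count. The conclusion is the same under both.

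The point is minor. A reader might infer that the safety conclusions or dose escalation are affected. They are not: DLTs are counted over the DLT period (protocol Table 13), SMC analyses have their own plan (SAP Section 4), and the events reach other outputs. The protocol synopsis reports 19 participants treated by 06 May 2021, so matching events to surgery dates by hand is feasible, though it should not be necessary.

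**What to change.** In SAP Section 15.2.1, redefine the third listing as: *All AEs (treatment-emergent or not) with onset from the day of surgery or delayed surgery to 42 days after.* Show the TEAE flag, the SAE flag and the surgery date in it.

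If a footnote on completeness is added, it should give no fixed figure, because step 6 shows that coverage depends on two dates that vary by participant. Suitable wording: *Unrelated non-serious AEs are recorded only to the end of short-term follow-up (protocol Section 8.3.1), so the 42-day window may be partly uncovered for such events, or wholly uncovered after late or delayed surgery, depending on the participant's surgery and Week 19 visit dates.*

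The cost is one changed filter, two existing flags and one existing date shown in a second listing, and an optional footnote. No new data collection is needed.
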